9.0 TREATMENT/INTERVENTION PLAN

9.1 Simulation

These simulation procedures generally represent our standard simulation procedures for comprehensive radiation therapy.

9.1.1 In order to develop a conformal treatment plan, all patients will undergo a CT simulation. IV contrast is not necessary for simulation.

9.1.2 All patients will undergo simulation in the treatment position with both upper extremities extended above their head using an Alpha Cradle (Alpha Cradle, Smithers Medical Products, North Canton, OH) or slant board immobilization.

9.1.3 The medial, lateral, superior, and inferior borders of any residual breast tissue and chest wall on the patient’s skin will be marked prior to simulation scanning.

9.1.4 Patients will be scanned from the base of skull through 5 cm below the clinically marked inferior port edge.

9.2 Virtual Simulation

9.2.1 The CT scan will be exported to a commercial virtual simulation software package. Normal structure and treatment volume contours will be delineated.

9.2.2 The following structures will be contoured with name allocation exactly as written in protocol. Standard contouring techniques in virtual simulation will be used to define these structures:

1. “Heart”
2. “The Planning Target Volume” (PTV)
3. “Contralateral breast”
4. “Thyroid”
5. “Right Lung”
6. “Left Lung”
7. “Humerus”
8. “Cord”

The PTV is defined as any residual breast tissue, chest wall, ipsilateral axillary lymph nodes, ipsilateral supraclavicular lymph nodes, ipsilateral infraclavicular lymph nodes, ipsilateral interpectoral lymph nodes, and ipsilateral internal mammary lymph nodes. Anatomic guidelines for defining these

boundaries have been extensively described by Dijkema et al(52). Several figures and a description of nodal boundary guidelines are included in Appendices 4 and 5.

9.3 Radiation Dose, Fractionation, Energy, and Parameters

9.3.1 The image and contour data will be exported to the treatment-planning system as appropriate where treatment planning and multi-beam IMRT optimization will occur. Optimization will be guided by the target tissue coverage and normal tissue avoidance parameters described below. All dose constraints must be within 2% of the given value.

9.3.2 The prescribed dose for all patients will be 5000 cGy in 25 fractions. 95% of the PTV will be prescribed to receive $\geq 95\%$ of the prescription dose. The maximum allowed heterogeneity will be limited to less than 5% of the PTV receiving greater than 110% of the prescription dose. Photons with energy of 6 MV will be used.

9.3.3 The following normal tissue limits will be used to optimize treatment planning. These limits were derived from a preliminary dosimetric study utilizing multi-beam IMRT treatment planning for comprehensive breast and nodal RT performed at Washington University(46).

Ipsilateral Lung V20	$\leq 30\%$
Ipsilateral Lung mean dose	≤ 2200 cGy
Contralateral Lung V20	$\leq 8\%$
Heart V25	$\leq 25\%$
Heart mean dose	≤ 2000 cGy
Heart maximum dose	≤ 5300 cGy

9.3.4 The number of gantry angles used for the multi-beam IMRT plan will be optimized for each patient but will generally range between six and twelve beams. The multi-beam IMRT plans will be delivered using dynamic multileaf collimators.

9.3.5 Some patients will receive a boost to part of the residual breast tissue. The decision to employ a boost will be made by the treating physician based on patient-specific criteria. The boost will be delivered sequentially, following multi-beam IMRT to the breast and regional lymph nodes.

9.4 Treatment Plan Evaluation

The treatment plan will be evaluated by the treating physician prior to treatment in order to ensure that all treatment parameters have been met. Isodose curves and dose volume histograms (DVH) will be analyzed. Evaluation criteria will include:

1. Isodose curves:
 - a. The 95% isodose line must generally conform to the PTV with visually acceptable target volume coverage and visually acceptable critical structure avoidance.
 - b. The 110% isodose line must not include any critical structure volumes.
2. Dose-Volume Histogram (DVH):

- a. The maximum allowed heterogeneity will be limited to less than 5% of the PTV receiving greater than 110% of the prescription dose.
- b. PTV DVH must meet all prescription parameters.
- c. Critical structure DVHs should meet constraint parameters (described in Section 9.3.3).

If a dosimetrically acceptable multi-field plan cannot be generated for an individual patient, she will be treated with our conventional technique of simplified IMRT.

9.5 Radiation Therapy Daily Treatments and Quality Assurance

9.5.1 Patients will receive external beam treatment once a day, 5 days a week for approximately 5 weeks. All missed radiation treatment visits will be made up. Daily set-up error will be minimized by the aforementioned clinically approved and commercially available patient setup techniques: AlignRT or KV imaging with orthogonal pair films will be performed. Generally, standard skin alignment marks are initially used to position patients. To increase accuracy of treatment delivery, AlignRT or KV films are subsequently taken. The patient is then shifted into the proper position and treatment is delivered.

10.0 EVALUATION DURING TREATMENT/INTERVENTION

Tests and Observation	Pre-Treatment	During IMRT	Completion of IMRT (CoT) ⁴	6-12 weeks after CoT	5-7 mo after CoT	Follow up ¹
History	X ²			X	X	X
Physical	X ²	X ⁵	X	X	X	X
(Feasible Plan Generated/Delivered)	X					
Daily Setup Data			X			
PFTs	X				X	
BMI	X					
Mammogram ³	X					X
Clinical Assessment of Acute Skin Toxicity		X ⁵	X	X		
Late Subcutaneous Fibrosis					X	X
Late Cutaneous Toxicity					X	X

Clinical Assessment of RP				X	X	X
RP CAP Questionnaire	X			X	X	X
BreastQ Questionnaire (for mastectomy patients)	X				X	
Pregnancy test (if relevant)	X					
¹ Patients will be seen at 12-14 months following the CoT and then every 6-8 months for up to 5 years of follow up. ² Done within 120 days of RT start ³ Mammogram at baseline and then annually or more often if clinically indicated (only applicable for lumpectomy patients). The annual mammogram will be based on the patient's last follow up mammogram (+/- 1 month window). For patients found to have distant metastasis after treatment, annual mammograms will no longer be required. ⁴ Done ±10 days of the last radiation treatment (CoT) ⁵ Done at least two times during radiation treatment including the CoT timepoint						

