1.0 PROTOCOL SUMMARY AND/OR SCHEMA

We propose a single-arm feasibility study utilizing multi-beam intensity-modulated radiation therapy (IMRT) in the adjuvant treatment of the breast and regional lymph nodes of women with node-positive breast cancer who require coverage of the internal mammary lymph nodes. Daily three-dimensional (3D) set-up verification will be performed prior to radiation treatment. The primary objective is to assess feasibility of multi-beam IMRT (feasibility is defined in detail below). Secondary objectives are to evaluate acute and late toxicities and locoregional recurrence associated with this treatment.

Consultation	Simulation	TX	FU

Patient Selection
 
 • Women with pathologically proven lymph node positive primary breast cancer requiring comprehensive radiation, including the internal mammary nodes (IMNs) • Status post definitive breast surgery and evaluation of axilla 
Pretreatment Evaluation
 
 • History and Physical (including calculation of BMI) • Community-Acquired Pneumonia Questionnaire • Pretreatment PFT 		
IMRT Administered
 
 • Daily setup data recorded • Skin toxicities evaluated during weekly visits 	
Follow-up +/- of skin (S), radiation pneumonitis (RP) and disease status (DS) at:
 
 • 6-12 weeks after completion of treatment (S, RP, DS) • 5-7 months after completion of treatment (S, RP, DS), Post treatment PFT • 12-14 months after completion of treatment (S, RP, DS) • Clinical Follow-up $\leq 5Y$

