10.1 Evaluations During Treatment

All patients will undergo an interview and physical examination a minimum of two times during radiation treatment. The maximum toxicities graded by CTCAE will be submitted to the Research Study Assistant at the Completion of IMRT Treatment (CoT). CoT is defined as within ten days of the last radiation treatment.

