12.2 Assessment of Secondary Objectives

Various metrics will be gathered at the following times: Pre-treatment (defined as within 45 days prior to the start of radiation treatment, excluding the History and Physical and mammogram), completion of therapy (done \pm 10 days of the last radiation treatment), 6-12 weeks following CoT, 5-7 months following CoT, and 12-14 months following CoT. These metrics are described below.

a. To evaluate the rate and severity of both acute and late cutaneous toxicity

The radiation oncologist will score cutaneous toxicity at the end of treatment (\pm 10 days of the last radiation treatment) and at 6-12 weeks following CoT. Late cutaneous toxicity will be scored at 5-7 months and 12-14 months following CoT, utilizing the CTCAE version 3.0 grading system. Some of these toxicities are not appropriately measured by the CTCAE and a more suitable scale is attached in Appendix 2.

b. To evaluate the rate and severity of late subcutaneous fibrosis

The radiation oncologist will score late subcutaneous fibrosis at 5-7 months and 12-14 months following CoT, utilizing the CTCAE version 3.0 grading system. Some of these toxicities are not appropriately measured by the CTCAE and a more suitable scale is attached in Appendix 2.

c. To evaluate the rate and severity of RP.

RP rates will be assessed by CTCAE version 3.0 grading system at 6-12 weeks, 5-7 months and at 12-14 months following CoT. We will also administer the CAP questionnaire pretreatment, at 6-12 weeks, 5-7 months and at 12-14 months following CoT. PFTs will be obtained at pretreatment and 5-7 months following CoT.

d. To evaluate local-regional control rates

Locoregional recurrence is defined as tumor in the ipsilateral breast/chest wall and/or ipsilateral regional lymph nodes (axillary, supraclavicular or internal mammary). Time to local recurrence will be calculated from the date of the completion of radiation treatment to the date of the biopsy proving recurrence or the first CT, PET, or MRI scan demonstrating recurrence. Kaplan-Meier methods will be used to assess local-regional control.

e. To evaluate patient set-up reproducibility in breast cancer patients treated with multi-beam IMRT using daily 3D position verification.

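### The minimum schedule for assessing acute skin toxicity is looser than the weekly visits in the schema, so the reported maximum grade can be understated and can rest on different numbers of looks per patient

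*Combined protocol and SAP*

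**What the plan says.** Four places in the combined protocol and SAP bear on how often acute skin toxicity is assessed.

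- Section 1.0 (schema), treatment column: "Skin toxicities evaluated during weekly visits".
- Section 10.0 table, footnote 5, attached to the acute skin toxicity row: "Done at least two times during radiation treatment including the CoT timepoint". Footnote 4 allows the CoT visit within ten days before or after the last fraction.
- Section 10.1: interview and examination "a minimum of two times during radiation treatment". It does not say whether CoT is one of the two. It also has the maximum CTCAE toxicities submitted at CoT.
- Section 12.2(a): "The radiation oncologist will score cutaneous toxicity at the end of treatment", and again at 6-12 weeks after CoT. No on-treatment scoring is listed there.

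Treatment length is given in Section 9.5: "Patients will receive external beam treatment once a day, 5 days a week for approximately 5 weeks". Section 14.0 plans to report the incidence of acute cutaneous toxicity with a 95% confidence interval.

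**The concern.** The reported quantity is a maximum, and a maximum depends on how many times one looks. Weekly visits over about five weeks give about five on-treatment looks. The Section 10.0 minimum gives one, plus CoT. No section says which visits feed the maximum submitted at CoT.

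Two things are at stake. First, a patient assessed at the minimum may pass through her worst grade between looks. Second, because the requirement is a floor, some patients may be graded five times and others twice, so their maxima are not on the same footing. The confidence interval planned in Section 14.0 reflects sampling error only and would show neither problem.

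The later visit is not a dependable backstop. Section 3.2.1 says acute effects generally settle within weeks of finishing radiation. Section 10.2 allows follow-up by telephone and drops whatever cannot be assessed that way.

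Rate and severity of acute cutaneous toxicity belongs to the first-listed secondary objective, and Section 2.2 intends these endpoints to inform the design of later studies.

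**Working it through.** The plan states no figure on this point, so there is none to reproduce. The check counts looks, establishes the direction of any error, and then illustrates its size under assumptions.

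**Counting looks.** Take day 1 as a Monday and 25 fractions on weekdays (Section 9.3.2 and Section 9.5). The last fraction is on day 4 × 7 + 5 = 33. Weekly Friday visits fall on days 5, 12, 19, 26 and 33, which is five looks. The Section 10.0 minimum is two looks, one of them CoT, which can fall from day 33 − 10 = 23 to day 33 + 10 = 43. If the 6-12 week visit is counted from the last fraction, the gap between CoT and that visit runs from 42 − 10 = 32 days to 84 + 10 = 94 days.

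**Direction.** If the visits actually used are a subset of a fuller set, the maximum over the subset is at most the maximum over the full set. Fewer looks can lower the reported grade or leave it unchanged, but cannot raise it.

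**Size, fixed calendar.** A peak starting at time t and lasting D is seen at visit v if t ≤ v < t + D. Assumptions not in the documents: onset uniform over days 15 to 33 (18 days), perfect grading, no recall between visits, and the next visit at 12 weeks.

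Example: for D = 7 with looks on days 19 and 33, onsets after day 12 up to 19, or after day 26 up to 33, are seen. Within days 15-33 that is 4 + 7 = 11 of 18 days, so 7/18 = 39% are missed. With the on-treatment look on day 12 the missed share is 11/18 = 61%; on day 26 it is 4/18 = 22%.

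| Peak duration | Weekly visits, missed | Minimum, CoT on day 33, missed | Minimum, CoT on day 23 or 43, missed |
|---|---|---|---|
| 7 days | 0% | 22-61% | 44-100% |
| 14 days | 0% | 0-22% | 17-78% |
| 21 days | 0% | 0% | 0-56% |

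Ranges are over the on-treatment look falling on day 12, 19 or 26.

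**Size, averaged over visit timing.** Here the share of peaks observed is simulated. The weekly schedule has looks at weeks 1 to 5 plus CoT. The minimum has one on-treatment look plus CoT. CoT is spread evenly around week 5. Entries are for peaks of 1 / 2 / 3 weeks.

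| Onset (weeks) | CoT spread | On-treatment look | Weekly + CoT | Minimum |
|---|---|---|---|---|
| 1.5-6 | ±10 days | random week | 84 / 85 / 85% | 34 / 59 / 73% |
| 2-5 | ±10 days | random week | 100 / 100 / 100% | 38 / 70 / 86% |
| 3-6 | ±10 days | random week | 76-78% | 40 / 61 / 68% |
| 3-5 | ±3 days | week 4 | 100 / 100 / 100% | 89 / 95 / 95% |
| 3-5 | ±3 days | random week | 100 / 100 / 100% | 56 / 92.5 / 96% |
| 4-6 | ±3 days | random week | about 55% | 47 / 51 / 51% |

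The largest gap is 100 − 38 = 62 percentage points. The smallest is about 4 (100 − 96, and 55 − 51).

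**The case against.** The strongest reply is that nothing here is contradictory. Sections 10.0 and 10.1 set floors, and a patient seen weekly meets both. A schema can describe the usual clinic rhythm while the table states the least that counts as compliance. Section 10.1 already asks for the maximum, naturally read as the worst grade over the visits held. Section 12.2(a) does not cancel the on-treatment assessments required elsewhere, and the table adds an acute skin assessment at 6-12 weeks. Nothing shows that the floor will be the practice. The study has one arm, so no comparison between arms can be distorted.

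Most of this stands. A reader might infer that the schema and Section 10.0 exclude each other. They do not. A reader might also infer that the schema demands a weekly CTCAE grade. It says that toxicity is evaluated, and weekly clinical review with a single submitted research grade is a coherent reading.

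A third tempting reading is that the peak will be understated by some particular amount. The documents give neither onset nor duration of the peak, and the results above run from small to large. With late onset (weeks 4-6) even weekly grading sees only about 55%, because many peaks begin after CoT, where on-treatment grading cannot help.

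What survives is narrower. The plan permits two looks, does not say which visits feed the maximum, and does not ask for the number of looks to be reported.

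**Conclusion.** The point holds as a minor one. The passages are unreconciled floors. A patient assessed only at the Section 10.0 minimum can have her maximum acute skin grade understated and never overstated, and patients can differ in how often they were looked at.

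The size is unknown. In the averaged scenarios the share of peaks observed falls by about 4 to 62 percentage points against weekly grading plus CoT. Single fixed calendars are wider still, from no loss (21-day peak, CoT on the last fraction) to complete loss (7-day peak, the only on-treatment look on day 12 and CoT on day 43). Every one of these figures rests on assumed onset, duration, visit week and CoT timing. They show sensitivity and are not estimates for this trial.

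A reader might infer a threat to the primary endpoint, since Section 12.1 counts treatment-related toxicity of grade 4 or higher. That would require a skin event of that grade to go unseen, and Section 14.0 expects grade 4 toxicity to be very rare. The effect is on a descriptive secondary endpoint.

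**What to change.** Bring Section 1.0, Section 10.0 footnote 5, Section 10.1 and Section 12.2(a) to one assessment schedule, and state whether CoT counts toward any minimum. Record the CTCAE skin grade at each on-treatment visit that the schema already describes. Define the acute cutaneous endpoint as the worst grade over those visits, CoT and the 6-12 week visit. Report the number of gradings per patient: taking the worst grade over visits held does not by itself equalise the looks, so the reader needs the count.

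This adds no visits beyond those in the schema. The cost is wording changes in four places and a little more data entry. It will not recover peaks that arise and resolve between CoT and the 6-12 week visit; that limitation should be stated with the results.

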10.1 Evaluations During Treatment

All patients will undergo an interview and physical examination a minimum of two times during radiation treatment. The maximum toxicities graded by CTCAE will be submitted to the Research Study Assistant at the Completion of IMRT Treatment (CoT). CoT is defined as within ten days of the last radiation treatment.

10.2 Evaluations After Treatment

Patients will have follow-up visits with physical examinations at 6-12 weeks, 5-7 months, and 12-14 months following the completion of radiation therapy. PFTs will be repeated at 5-7 months following CoT. Mammograms will be obtained annually (for patients with intact breasts) or more frequently if clinically indicated. The annual mammogram will be based on the patient's last follow up mammogram with a +/- 1 month window. For patients found to have distant metastasis after treatment, annual mammograms will no longer be required.

More frequent follow-up visits are at the discretion of the treating physician. After the follow-up visit that occurs 12-14 months after CoT, patients will be seen at a minimum of every 6-8 months until 5 years of follow up after CoT. The patient will be asked to complete the CAP questionnaire at each follow up visit when she sees the radiation oncologist.

Patients who cannot make their follow-up appointments have the option of conducting these visits over the phone. Visit requirements that cannot be assessed by phone will be eliminated for these visits. However, the 5-7 month PFT must be completed.

10.4 Evaluations of Early and Late Toxicity

The CTCAE version 3.0 scale will be used. The portions of the CTCAE relevant to this study are available in Appendix 1. The grading scale for other toxicities that are not appropriately measured by CTCAE is available in Appendix 2.

11.0 TOXICITIES/SIDE EFFECTS

Patients will be assessed for toxicities related to radiation treatment. Potential acute side effects include skin reactions, erythema, edema, hyperpigmentation, desquamation, fatigue, and/or RP. The incidences of these side effects with conventional radiation techniques to the breast and lymph nodes are described in Section 3.2.1.

Lactating and pregnant women are also excluded because of potential teratogenic effects of radiotherapy that may be harmful to the developing fetus or nursing infant.

Patients will be assessed for late toxicities (>3 months post radiation) as described in Section 3.2.2, including skin toxicity and/or RP. Toxicities will be scored according to the CTCAE, version 3.0 criteria.

No side effects are expected to result from the daily imaging used for target localization.

12.2 Assessment of Secondary Objectives

Various metrics will be gathered at the following times: Pre-treatment (defined as within 45 days prior to the start of radiation treatment, excluding the History and Physical and mammogram), completion of therapy (done \pm 10 days of the last radiation treatment), 6-12 weeks following CoT, 5-7 months following CoT, and 12-14 months following CoT. These metrics are described below.

a. To evaluate the rate and severity of both acute and late cutaneous toxicity

The radiation oncologist will score cutaneous toxicity at the end of treatment (\pm 10 days of the last radiation treatment) and at 6-12 weeks following CoT. Late cutaneous toxicity will be scored at 5-7 months and 12-14 months following CoT, utilizing the CTCAE version 3.0 grading system. Some of these toxicities are not appropriately measured by the CTCAE and a more suitable scale is attached in Appendix 2.

b. To evaluate the rate and severity of late subcutaneous fibrosis

The radiation oncologist will score late subcutaneous fibrosis at 5-7 months and 12-14 months following CoT, utilizing the CTCAE version 3.0 grading system. Some of these toxicities are not appropriately measured by the CTCAE and a more suitable scale is attached in Appendix 2.

c. To evaluate the rate and severity of RP.

RP rates will be assessed by CTCAE version 3.0 grading system at 6-12 weeks, 5-7 months and at 12-14 months following CoT. We will also administer the CAP questionnaire pretreatment, at 6-12 weeks, 5-7 months and at 12-14 months following CoT. PFTs will be obtained at pretreatment and 5-7 months following CoT.

d. To evaluate local-regional control rates

Locoregional recurrence is defined as tumor in the ipsilateral breast/chest wall and/or ipsilateral regional lymph nodes (axillary, supraclavicular or internal mammary). Time to local recurrence will be calculated from the date of the completion of radiation treatment to the date of the biopsy proving recurrence or the first CT, PET, or MRI scan demonstrating recurrence. Kaplan-Meier methods will be used to assess local-regional control.

e. To evaluate patient set-up reproducibility in breast cancer patients treated with multi-beam IMRT using daily 3D position verification.

Standard skin marks for positioning patients for external beam radiation therapy will be applied during the simulation process. These marks will be used by radiation therapists to initially position patients in the treatment unit. AlignRT or KV imaging with orthogonal films will then be taken and used to accurately position the patient for treatment. The difference in initial set up and final set up will be recorded in mm on a daily basis. Basic descriptive statistics will be tabulated after the CoT.

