3.2 Toxicities of Comprehensive Radiation Therapy

3.2.1 Acute Toxicities

The toxicity of comprehensive radiation therapy has been well described (15). Acute toxicity is defined as those effects that occur during a course of radiation therapy or within 90 days of its completion. Essentially all patients experience skin erythema, which may progress to desquamation in a fraction of patients. A mild pharyngitis is rarely seen. Fatigue can develop in up to 40% of patients. Acute side effects generally resolve within several weeks of the completion of radiation therapy and only rarely cause a treatment interruption. Acute toxicities to the skin and pharynx are typically graded using the CTCAE version 3. Relevant sections of the CTCAE are included in Appendix 1.

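### The completion-of-treatment skin score and the maximum-toxicity submission may be made up to 10 days before radiation ends, so a later, transient skin reaction can enter no required score

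*Combined protocol and SAP*

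**What the plan says.** Section 12.2(a) sets the times of the acute skin scores: "The radiation oncologist will score cutaneous toxicity at the end of treatment (\pm 10 days of the last radiation treatment) and at 6-12 weeks following CoT". Footnote 4 to the schedule in Section 10.0 repeats the two-sided window for the completion visit: "Done ±10 days of the last radiation treatment (CoT". Section 10.1 makes the completion time point itself a range: "CoT is defined as within ten days of the last radiation treatment", without saying before or after. It also ties the summary toxicity record to it: "The maximum toxicities graded by CTCAE will be submitted to the Research Study Assistant at the Completion of IMRT Treatment (CoT".

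The required number of examinations is small. Section 10.1 sets a minimum of two during treatment, and footnote 5 in 10.0 counts the CoT visit as one of them. The schema in Section 1.0 instead speaks of weekly skin evaluation. After CoT, the next scheduled skin score is at 6–12 weeks.

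Section 3.2.1 defines acute toxicity as running from the start of the course to 90 days after it ends, and says: "Acute side effects generally resolve within several weeks of the completion of radiation therapy". Section 14.0 plans incidences with 95% confidence intervals for cutaneous toxicity. It does not say which time point is used or whether the worst grade is taken.

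**The concern.** A window placed symmetrically around the last fraction opens before treatment is complete. A grade taken in its early half describes a patient who has not had the full dose, yet it is filed as the completion score, and the maximum grade may be submitted on the same occasion. If the reaction worsens later and settles before the 6–12 week visit, the record is complete and compliant but shows a lower maximum than the patient had. The error runs in one direction only: a transient peak can be lost, but none can be invented.

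Acute cutaneous toxicity is part of the first secondary objective in Section 2.2, and that section says these endpoints are to inform the design of later studies. A rate that is too low, and that pools patients scored before and after full dose as one time point, would be a weak basis for that.

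**Working it through.** **Inputs.** Section 9.3.2: "The prescribed dose for all patients will be 5000 cGy in 25 fractions", so 5000/25 = 200 cGy (2 Gy, or 4% of the dose) per fraction. Section 9.5.1: "Patients will receive external beam treatment once a day, 5 days a week for approximately 5 weeks". Check on the stated course length: 25 fractions / 5 per week = 5.0 weeks, which agrees.

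**Fractions still to come at day −10.** Let r be the number of weekday fractions after day −10, with the last fraction on day 0. Dose outstanding = 2 Gy × r; share = r/25. Assume calendar days, no missed treatments and no boost.

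| Last fraction on | Day −10 is a | r | Dose outstanding | Share |
|---|---|---|---|---|
| Monday | Friday | 6 | 12 Gy | 24% |
| Tuesday | Saturday | 7 | 14 Gy | 28% |
| Wednesday | Sunday | 8 | 16 Gy | 32% |
| Thursday | Monday | 8 | 16 Gy | 32% |
| Friday | Tuesday | 8 | 16 Gy | 32% |

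Where day −10 falls on a weekend, the earliest weekday visit is day −8 (Tuesday finish, 6 left, 24%) or day −9 (Wednesday finish, 7 left, 28%), so the range stays 24–32%. If the visit comes before that day's fraction, one more remains in each case: 7 to 9 fractions, 28–36%. At a visit on or after day 0 the share is 0%.

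**Effect of a boost.** Section 9.3.5 allows a sequential boost without giving its number of fractions. If the last radiation treatment includes the boost, 6 to 8 fractions still remain at day −10, but fewer of them belong to the main course:
- assumed 5-fraction boost: 6−5 to 8−5 = 1 to 3 of the 25 main fractions (4–12%); of all 30 fractions, 6/30 to 8/30 = 20–27%;
- assumed 8-fraction boost: none of the main fractions; of all 33 fractions, 6/33 to 8/33 = 18–24%.

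**Interval without a required skin score.** From day −10 to the 6–12 week visit, counted from the last fraction: 10 + 42 = 52 days to 10 + 84 = 94 days.

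**A compliant record (hypothetical).** Last fraction on a Friday. First examination in week 2, grade 1. CoT examination on the Tuesday of week 4 (day −10), after 17 fractions (34 Gy), grade 1, and the maximum is submitted. The reaction reaches grade 2 in the week after treatment and has resolved by week 6. The 6–12 week score is grade 0. Every required score has been made and the maximum on file is grade 1, although under Section 3.2.1 the acute toxicity was grade 2. Nothing in 10.1, 12.2 or 14.0 requires a later grade to update the submission, or asks at 6–12 weeks for the worst grade since CoT.

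**The case against.** The strongest reply is that practice will be better than the minimum. The schema has skin evaluated weekly. With weekly visits one falls among the last five treatment days, when at most 4 fractions remain after it (4/25 = 16%), and 10.1 does ask for a maximum, not a single reading. This lowers the risk materially. It does not remove it: 10.0 and 10.1 bind the site only to two examinations including CoT, and no text links a visit after the submission to the submitted maximum. The schema and these sections need to be reconciled in any case.

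Second, the 6–12 week visit follows the full dose and includes a history. That stands for reactions still present then. For reactions that have gone, the history helps only if someone is asked to grade from it, and the plan does not ask.

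Third, the consequence is limited. Section 2.2 calls these endpoints descriptive, and no comparison or decision rule uses the skin grade. The infeasibility criteria in 12.1(b) count events up to the 5–7 month follow-up and are not tied to the CoT window. This stands in full.

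A reader might infer that the endpoint as a whole leaves out a quarter to a third of the dose. The documents do not support that: the figure belongs to a visit at the very start of the window. A reader might also want a percentage of peaks missed. That would need the onset and duration of the reaction and the distribution of visits within the window, none of which the documents give.

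**Conclusion.** The point holds as a flaw in the placement of the assessment window. The plan allows the completion skin score and the maximum-grade submission before treatment has ended. At the extreme, 6 to 8 of 25 fractions (24–32%) are outstanding, assuming a visit on day −10, calendar days, no missed treatments and no boost. A boost counted in the last radiation treatment, or a later visit, makes the share of the main course smaller. The resulting bias in the acute cutaneous toxicity rate is downward; its size cannot be derived from the documents.

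It would also be too strong to infer that the primary feasibility result is at risk, or that moving the window alone cures the problem. A score taken on the day of the last fraction still misses a reaction that peaks afterwards and settles before week 6. This is a cheap improvement to a descriptive secondary endpoint, not a defect that threatens the study.

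**What to change.** 1. In 10.0 footnote 4, 10.1 and 12.2, let the CoT assessment window run from the day of the last radiation treatment to 10 days after it.
2. In 10.1, define CoT as the date of the last radiation treatment, so that later visit windows count from one date, and say whether a boost is included.
3. Submit the maximum acute grade only after the CoT assessment. Define it as the worst grade over all on-treatment visits, the CoT assessment and the 6–12 week visit, using the history already scheduled there to grade any reaction since CoT, and update the record at that visit.
4. In 14.0, state that the acute cutaneous incidence is based on this worst grade.

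The changes are to wording and to one form. They have a cost in practice: some more window deviations, and an assessment after the day of the last fraction may need a return visit or phone contact. Scoring on the last treatment day avoids that but leaves later peaks unseen, which is why the worst-grade record at 6–12 weeks is needed as well. Grades based on recall will be less exact than examined grades and should be marked as such.
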